4. To evaluate the influence of various adjuvants on cellular immune responses.
5. Describe mucosal humoral responses across vaccination regimens in cervicovaginal and rectal secretions and semen.

Exploratory

1. Characterize B-cell functional specificities for each vaccination regimen.
2. Characterization of innate immunity.
3. Assess the innate/gene expression induced across vaccination regimens (DNA microarray, RNA sequencing) to compare relative influence of various

adjuvants in the gene expression profiles sorted T cell, B cell, and innate cell subsets.

4. Perform systems serology analyses.

Sub-objective

In participants who elect to undergo lymph node biopsy, characterize HIV-specific responses, T cell activation, T follicular helper (Tfh) cell and B cell distribution in intact lymph nodes (excision of intact peripheral inguinal lymph node) at weeks 14 and 58.

Duration of Individual Subject Participation

Each participant will be enrolled for 108 weeks (105 weeks of clinic visits and then contact by phone once weekly for an additional three weeks to inquire about medically attended adverse events).

Estimated Time to Last Subject/Last Visit

Approximately 137 weeks (about 2 years, 8 months)

LAY SUMMARY

The Kenya Medical Research Institute (KEMRI) in collaboration with the U.S. Military HIV Research Program (MHRP) is conducting a study on HIV vaccines. A vaccine is a medical product given to prevent certain diseases, most often infectious diseases. The vaccine may educate the human body to form a defensive response to try to prevent the disease from the beginning or taking hold of the body. This defensive response called the immune response, and it is the body's way to fight infections.

The experimental HIV vaccines tested in this study are Env-C Plasmid DNA and HIV Env gp145 C.6980 protein given with different adjuvants to increase the immune response. An adjuvant is a substance added to vaccines that can help to make the vaccine more effective by improving the immune response or causing the immune response to last longer than without the adjuvant. These adjuvants are mixed with the vaccines and injected into the muscle or placed on top of the skin. The HIV vaccines contain a piece of genetic material or a protein copied from the HIV virus cover (Env), but they do not contain the virus itself. The vaccines cannot cause HIV infection or Acquired Immune Deficiency Syndrome (AIDS).

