An SAE: An adverse event or suspected adverse reaction is considered "serious" if, in the view of either the investigator or sponsor, it results in any of the following outcomes: death, a life-threatening adverse event, inpatient hospitalization or prolongation of existing hospitalization, a persistent or significant incapacity or substantial disruption of the ability to conduct normal life functions, or a congenital anomaly/birth defect. Important medical events that may not result in death, be life-threatening or require hospitalization may be considered serious when, based upon appropriate medical judgment, they may jeopardize the participant and may require medical or surgical intervention to prevent one of the outcomes listed in this definition. Examples of such medical events include allergic bronchospasm requiring intensive treatment in an emergency room or at home, blood dyscrasias or convulsions that do not result in inpatient hospitalization, or the development of drug dependency or drug abuse (21 CFR 312.32).

"Life-threatening" refers to an adverse event that at occurrence represents an immediate risk of death to the participant. An event that may cause death if it occurs in a more severe form is not considered life-threatening. Similarly, hospital admission for an elective procedure is not considered an SAE. The clinician will ask each participant about other interim adverse experiences and record this information in the source documents. Study staff will enter AE or SAE information into the study database within three business days of the participant visit. After study day 28 after the last vaccination, only SAEs and new chronic medical conditions that require ongoing medical management will be entered into the database, through the last study visit. All other adverse events will be recorded on source documents only. The PI or designee will assess the relationship of the study product to the events.

If an event meets both the criteria of a study endpoint and an adverse event, the event will be reported either as a study endpoint or as an adverse event (not both).

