8.1.6 MEDICALLY ATTENDED ADVERSE EVENTS

The FDA requests that clinical trials of preventive vaccines with adjuvants such as ALF43 and dmLT provide for collection and analysis of data relating to medically attended adverse events (MAAEs) among subjects in all treatment groups through 12 months or longer following the last study vaccination, due to the theoretical potential for induction of autoimmune or auto-inflammatory diseases.

MAAEs are defined as AEs with medically attended visits including hospital, emergency room, urgent care clinic, or other visits to or from medical personnel for any reason. Adverse events (e.g., abnormal vitals) identified at a routine study visit will not be considered MAAEs.

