8.1.8 ADVERSE EVENT DOCUMENTATION

The clinician will ask each participant about other interim adverse experiences and record this information in the source documents. Study staff will enter data into the study database within three business days of participant visits. 28 days after the last vaccination, only SAEs and new chronic medical conditions that require ongoing medical management will be entered into the database, through the last study visit. All other adverse events will be recorded on source documents only. The PI or designee will assess the relationship of the study product to the events. Participants will be asked for their consent for photography if the clinician wishes to document an unusual or unexpected finding.

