16 APPENDICES

APPENDIX A. SCHEDULE OF EVALUATIONS

Visit Number	S1	1	2	3	4	5	6	7	8	9	10	11	12	13	14	15	16	17	18	19	20	21	22	23	24	25	26 Exit	
Visit Day	-45 to -3	0	3 ± 1	7 ± 2	14 ± 3	28 ± 7	35 ± 2	42 ± 3	84 ± 7	87 ± 1	91 ± 2	98 ± 3	140 ± 7	143 ± 1	147 ± 2	154 ± 3	224 ± 7	231 ± 2	238 ± 3	392 ± 7	395 ± 1	399 ± 2	406 ± 3	476 ± 14	560 ± 14	728 ± 14	735 ± 14	
Visit week		0	0.5	1	2	4	5	6	12	12.5	13	14	20	20.5	21	22	32	33	34	56	56.5	57	58	68	80	104	105	
Clinical																												
Briefing & contact information	X																											
Informed consents	X																											
Test of understanding	X																											
Complete physical exam, height, weight & review medical history	X																											
Vital signs (BP, pulse, RR, oral temp)	X	X	X	X	X	X	X	X	X	X	X	X	X	X	X	X	X	X	X	X	X	X	X	X	X	X		
Concomitant Medication	X	X	X	X	X	X	X	X	X	X	X	X	X	X	X	X	X	X	X	X	X	X	X	X	X	X		
Targeted physical exam and review of symptoms	X	X	X	X	X	X	X	X	X	X	X	X	X	X	X	X	X	X	X	X	X	X	X	X	X	X		
HIV risk counseling; pregnancy counseling ¹¹	X	X	X	X	X	X	X	X	X	X	X	X	X	X	X	X	X	X	X	X	X	X	X	X	X	X		
Vaccination¹³	X ⁶			X ⁶		X ⁶		X ⁶		X ⁶		X ⁶		X ⁶		X ⁶		X ⁶		X ⁶		X ⁶		X ⁶		X ⁶		
Review Eligibility	X			X			X			X			X			X		X		X		X		X		X		
Enrollment and randomization ¹²	X																											
Assess reactogenicity in clinic 30-60 min post-vaccination	X			X			X			X			X			X		X		X		X		X		X		
MAAE documentation ⁹	X	X	X	X	X	X	X	X	X	X	X	X	X	X	X	X	X	X	X	X	X	X	X	X	X	X		
Adverse Event documentation	X	X	X	X	X	X	X	X	X	X	X	X	X	X	X	X	X	X	X	X	X	X	X	X	X	X		
Diary card completion/review ¹⁰		X	X		X		X		X	X		X	X		X	X		X		X	X		X	X				
Clinical Laboratory Assessments⁵																												
Urinalysis dipstick for blood, protein and glucose	X																											
Urine-pregnancy test ⁷	X	X			X		X	X		X ²	X		X	X		X	X		X ²	X	X	X		X	X	X		
CBC with differential	3		3			3			3			3			3			3			3			3				
Creatinine, ALT, AST	3		3			3			3			3			3			3			3			3				
Syphilis serology	6																											
HBsAg/HepC	NB																											
Pap smear for Softcup collection participants	X																											
Coagulation and safety tests prior lymph node biopsy ⁸																												
HIV testing with Pre/Post HIV test counseling	6	6																								6	6	
Research Laboratory Assessments³																												
HIV NAb		6		6	6	6	6	6	6	6	6	6	6	6	6	6	6	6	6	6	6	6	6	6	6	6	6	

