7: Pregnancy testing must be performed prior to vaccination and mucosal secretion collection

8: 9ml should be taken if CBC/Chem results not available on day of biopsy. Otherwise, 3ml should be drawn

9: Medically Attended Adverse Events will be followed through the end of the study, a full 12 months following the last vaccination

10: Participants will take home the diary card and complete and the diary card will be reviewed at 7 days after vaccination.

11: Additional testing as clinically indicated

12: A participant is considered enrolled into the study once they are randomized into a study group

13: Study vaccination outside of a participant's vaccination window may occur at the discretion of the PSRT.

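### The day-28 database cut-off keeps non-serious, non-chronic medically attended adverse events out of the database for 48 of the 52 weeks in which the protocol follows them

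*Protocol*

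**What the plan says.** Section 8.1.3 sets this rule for the time once day 28 after the final dose has passed: "only SAEs and new chronic medical conditions that require ongoing medical management will be entered into the database, through the last study visit". It continues: "All other adverse events will be recorded on source documents only". Section 8.1.8 repeats the rule: "28 days after the last vaccination, only SAEs and new chronic medical conditions that require ongoing medical management will be entered into the database". Neither section mentions MAAEs.

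Section 8.1.6 says that the FDA asks trials of vaccines with adjuvants such as ALF43 and dmLT to "provide for collection and analysis of data relating to medically attended adverse events (MAAEs) among subjects in all treatment groups through 12 months or longer" after the last vaccination. The reason given is the theoretical risk of autoimmune or auto-inflammatory disease. The definition there begins: "MAAEs are defined as AEs with medically attended visits including hospital, emergency room, urgent care clinic".

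The schedule in Appendix A has a separate row, "MAAE documentation", with footnote 9: "Medically Attended Adverse Events will be followed through the end of the study, a full 12 months following the last vaccination". The Protocol Summary adds "contact by phone once weekly for an additional three weeks to inquire about medically attended adverse events" after the clinic visits end, and the Precis says the same.

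**The concern.** By the definition in 8.1.6 an MAAE is an adverse event. If it is neither serious nor a new chronic condition, it falls into the residual class that 8.1.3 and 8.1.8 send to source documents. The protocol therefore extends follow-up to a full year for MAAEs, and then has no database route for part of that category over most of the year. An analysis plan cannot repair this, because it can only work with records that were entered.

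The year matters more here than in a trial of established products. Section 2.2.2 says ALF43 has not been used in humans, and section 2.2.3.5 says this is the first trial of dmLT by the transcutaneous route. A medical visit for a symptom not yet diagnosed as chronic or immune-mediated is what the MAAE category can catch and the retained categories may miss.

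Two smaller points lie alongside:

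- **Primary analysis (7.2.2).** It says that adverse events are recorded to the end of the trial and tabulated, but not that database capture of non-serious, non-chronic events stops at day 28. Related adverse events are part of the primary endpoint (1.2.1 and 2.7.1), so late related events of this kind are affected too.
- **Closing calls (5.5).** The listed questions cover vital status, life-threatening events, disability, hospitalization, HIV diagnosis and pregnancy. None asks about a medical visit short of hospitalization, although asking about MAAEs is the stated purpose of the calls.

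**Working it through.** **Inputs (all nominal)**

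- Last vaccination: week 56, day 392 (Table 1; Appendix A, visit 19).
- Database cut-off: 28 days after the last vaccination (8.1.3, 8.1.8).
- Exit clinic visit: week 105, day 735 (Appendix A, visit 26).
- End of contact: three weekly calls after the exit visit, to week 108 (Protocol Summary, 5.5).

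**The protocol's own figure**

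- End of contact: 735 + 3 × 7 = day 756, and 108 × 7 = 756, so the two routes agree.
- Time from last dose to end of contact: 756 − 392 = 364 days = 52 weeks. This reproduces the 12 months in Appendix A, footnote 9.

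**The gap**

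| Quantity | Calculation | Result |
|---|---|---|
| Cut-off | 392 + 28 | day 420 (week 60) |
| Days with database entry of all AEs | 420 − 392 | 28 days (4 weeks) |
| Days after the cut-off | 756 − 420 | 336 days (48 weeks) |
| Share of the 364 days | 336 / 364 | 92.3% |
| of which clinic follow-up | 735 − 420 = 315; 315 / 364 | 86.5% |
| of which telephone only | 756 − 735 = 21; 21 / 364 | 5.8% |

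Visit 22 (day 406) is the last before the cut-off. Visits 23 to 26 (days 476, 560, 728 and 735), 4 of the 26 numbered visits, come after it, as do all three calls.

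**Which events are affected after day 420**

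| Event | Entered in the database? |
|---|---|
| MAAE that is an SAE | Yes (8.1.3, 8.1.8) |
| MAAE that is a new chronic condition needing continuing management | Yes (8.1.3, 8.1.8) |
| MAAE on the list of potentially immune-mediated conditions | Expedited report (8.2.1.1, 8.2.1.3); database entry not stated unless serious or chronic |
| Any other MAAE | No; source documents only |

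Only the last row is lost to the database altogether.

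**The case against.** The best defence is that the text is silent rather than contradictory. Footnote 9 promises only that MAAEs will be followed, and recording them on source documents meets that promise. Section 8.1.6 reports what the FDA requests and does not itself commit to database entry or to an MAAE analysis. MAAEs also have their own section and their own schedule row, so they could be read as a separate stream with its own form, leaving 8.1.3 and 8.1.8 to govern ordinary adverse events. An earlier paragraph of 8.1.3 says all adverse events are documented as source for the electronic case report form. Finally, the events most relevant to autoimmunity are largely kept through the SAE, chronic-condition and expedited-reporting routes.

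Part of this stands. A separate MAAE form may exist, because case report form content is not shown. The retained categories do cover much of the autoimmune concern. A 28-day window for ordinary adverse events is not wrong in itself, and it applies to every group alike, so it creates no evident between-group bias. Recording on source documents also meets 7.2.2 literally.

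The rest does not remove the problem. The schedule row only schedules documentation. The general sentence in 8.1.3 is followed by a specific rule worded as exclusive, and 8.1.8 repeats that rule. MAAEs are defined as adverse events, and no section says they are entered after the cut-off. The request that 8.1.6 cites is for collection and analysis of MAAEs, not of their serious or chronic subset.

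**Conclusion.** The concern holds. Followed as written, 8.1.3 and 8.1.8 keep non-serious, non-chronic MAAEs out of the database from day 420 to day 756, which is 336 of the 364 days that the protocol sets aside for following them. This defeats the purpose stated in 8.1.6 and should be fixed.

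The size is elapsed time on the nominal schedule for a participant who receives all six doses. No event count can be given, because the protocol states no MAAE rate. The clock starts at the last vaccination, so a participant who stops vaccination early but stays in follow-up (after pregnancy, for example, under 4.4.4) has a longer gap. The figure takes the cut-off by date of onset. If it runs by date of entry instead, an event that begins before day 420 but is first reported at the day-476 visit is also left out.

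The conclusion assumes that no instruction outside the protocol sends MAAEs to the database after the cut-off. If one does, the protocol text still needs to be brought into line with it. The missing item in the telephone list is a separate, smaller fault: it concerns what is asked, not what is entered.

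**What to change.** 1. **Sections 8.1.3 and 8.1.8.** Replace the rule with wording such as: *From day 28 after the last vaccination through week 108, the database will receive SAEs, MAAEs, PIMMCs, AEs judged related to study product, and new chronic conditions needing continuing medical management. Other AEs will be kept on source documents.* MAAEs are the necessary addition. PIMMCs are added to match their expedited reporting, and related AEs to match the primary endpoint.
2. **Section 7.2.2.** State the capture window for each category of adverse event that is tabulated.
3. **Section 5.5.** Add to the telephone list an item on any medically attended visit and its reason.

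The cost is wording in four sections and modest extra entry of events that are largely on source documents already. The 28-day window can stay for non-serious events that were unrelated, not medically attended and not otherwise listed. Visits and clinical procedures do not change. The change is best made before data entry closes, so that late MAAEs already on source documents can be entered.

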8.1.4 SERIOUS ADVERSE EVENTS (SAEs)

An adverse event or suspected unexpected adverse reaction (SUSAR) is considered "serious" if, in the view of either the investigator or sponsor, it results in any of the following outcomes:

- Results in death,
- Is life-threatening,
- Requires inpatient hospitalization or prolongation of existing hospitalization,

- Results in persistent or significant disability/incapacity,
- Is a congenital anomaly/birth defect
- Is an important medical event that may not be immediately life-threatening or result in death or hospitalization but may jeopardize the patient or may require intervention to prevent one of the other outcomes listed in the definition above.

Important medical events that may not result in death, be life-threatening, or require hospitalizations may be considered serious when, based upon appropriate medical judgment they may jeopardize the participant and may require medical or surgical intervention to prevent one of the outcomes listed in this definition. Examples of such medical events include allergic bronchospasm requiring intensive treatment in an emergency room or at home, blood dyscrasias or convulsions that do not result in inpatient hospitalization, or the development of drug dependency or drug abuse.

Life-threatening adverse event: An AE is considered “life-threatening” if, in the view of either the site principal investigator or sponsor, its occurrence places the participant at immediate risk of death. It does not include an AE that, had it occurred in a more severe form, might have caused death.

SAEs will be assessed for severity and relationship to study product and alternate etiology (if not related to study product) by the PI or AI listed on the Form FDA 1572 and followed through resolution.

8.1.5 POTENTIALLY IMMUNE-MEDIATED MEDICAL CONDITIONS (PIMMCs)

PIMMCs constitute a group of AEs that includes diseases which are clearly autoimmune in etiology and other inflammatory and/or neurologic disorders which may or may not have autoimmune etiologies.

8.1.6 MEDICALLY ATTENDED ADVERSE EVENTS

The FDA requests that clinical trials of preventive vaccines with adjuvants such as ALF43 and dmLT provide for collection and analysis of data relating to medically attended adverse events (MAAEs) among subjects in all treatment groups through 12 months or longer following the last study vaccination, due to the theoretical potential for induction of autoimmune or auto-inflammatory diseases.

MAAEs are defined as AEs with medically attended visits including hospital, emergency room, urgent care clinic, or other visits to or from medical personnel for any reason. Adverse events (e.g., abnormal vitals) identified at a routine study visit will not be considered MAAEs.

8.1.7 ADVERSE EVENT ASSESSMENT

All AEs (laboratory and clinical symptoms) will be graded for severity and assessed for relationship to study product using the DAIDS Table for Grading the Severity of Adult and Pediatric Adverse Events (DAIDS AE Grading Table), Version 2.1 dated July 2017 that is found on the website <https://rsc.niaid.nih.gov/clinical-research-sites/daids-adverse-event-grading-tables>. AEs characterized as intermittent require documentation of onset and duration of each episode.

The start and stop date of each reported AE will be recorded on the appropriate data collection form and eCRF. Changes in the severity of an AE will be documented to allow an assessment of the duration of the event at each level of intensity. Adverse events not identified in the grading table, follow the guidelines provided at the beginning of the table.

8.1.8 ADVERSE EVENT DOCUMENTATION

The clinician will ask each participant about other interim adverse experiences and record this information in the source documents. Study staff will enter data into the study database within three business days of participant visits. 28 days after the last vaccination, only SAEs and new chronic medical conditions that require ongoing medical management will be entered into the database, through the last study visit. All other adverse events will be recorded on source documents only. The PI or designee will assess the relationship of the study product to the events. Participants will be asked for their consent for photography if the clinician wishes to document an unusual or unexpected finding.

8.1.8.1 Severity vs. Seriousness of Adverse Events

The term “severity” describes the intensity of a specific event. The severity of a specific event is graded, i.e., mild (Grade 1), moderate (Grade 2), severe (Grade 3), potentially life-threatening (Grade 4), or death (Grade 5) using the DAIDS AE Grading Table Version 2.1. The severity of an AE does not determine whether an event meets the definition of seriousness, which is based on participant/event outcome or action criteria associated with events that pose a threat to a participant’s life or functioning (ICH E2A).

8.1.8.2 Relationship to Study Product

The site investigator is responsible for assessing the relationship between the AE and the study agents. Site investigators must determine whether there is a reasonable possibility that the study agents caused or contributed to a and AE or SAE. The relationship assessment, based on clinical judgment, often relies on the following:

- A temporal relationship between the event and administration of the study agents,
- A plausible biological mechanism for the agent to cause the AE,
- Another possible etiology for the AE,
- Previous reports of similar AEs associated with the study agent or other agents in the same class, and
- Recurrence of the AE after re-challenge or resolution after de-challenge, if applicable.

The terms used to assess the relationship of an event to study agent are:

Related – There is a reasonable possibility that the AE may be related to the study agents.

Not Related – There is not a reasonable possibility that the AE is related to the study agents.

When a SAE is assessed as “not related” to study agents, an alternative etiology, diagnosis, or explanation for the SAE should be provided. If new information becomes available, the relationship assessment of any AE should be reviewed again and updated, as required.

When the study agent is a fixed dose combination agent, an assessment of attribution will be made for each component and the combination agent.

